2.5 Exploratory Objectives

The objectives of the correlative studies are to determine:

- 2.5.1 whether and to what extent CD30 expression predicts for response and outcome
- 2.5.2 whether and to what extent expression of EBV markers predicts for response and outcome
- 2.5.3 whether changes in serum levels of EBV correlate with response and subsequent loss of response to therapy
- 2.5.4 Collect and store peripheral blood samples for future, unspecified use (phase II patients only).

2.6 Exploratory Endpoints

Levels of CD30 expression, EBV proliferation, and tumor proliferation (ie, Ki-67), all obtained from TMAs performed on pre-treatment tissue samples, will be correlated with ORR, as well as with EFS at one year. Quantitative serum EBV levels will be monitored for the duration of treatment, and change in levels correlated with ORR, duration of response, and progression of disease.

3.1 Inclusion Criteria

- 3.1.1 Patients must have a histologically confirmed CD20+ lymphoproliferative disease that is related to an immunosuppressed state (e.g., PTLD, DLBCL of the elderly, iatrogenic immunodeficiency-associated LPD) and for which rituximab monotherapy would be considered to be appropriate frontline therapy.
- 3.1.2 In cases of lymphoproliferative disease arising in patients who are pharmacologically immunosuppressed, reduction of immunosuppression (RI) must be attempted prior to or in conjunction with enrollment, with the exception of those for whom RI would pose excessive threat of clinically significant graft rejection (as judged by local investigator).

NOTE: Patients who are otherwise immunosuppressed (for reasons such as immune dysregulation related to autoimmune conditions, in the absence of pharmacological immunosuppression) may be eligible if, in the opinion of the treating investigator, the risk of immediate treatment with R-CHOP outweighs the benefit for these patients.

- 3.1.3 Patients must have bi-dimensionally measurable disease (at least 1 cm).
- NOTE: Patients with fully resected disease are eligible, and will be evaluable for all toxicity and efficacy endpoints except objective response.*
- 3.1.4 Patients must be ≥ 18 years of age.
- 3.1.5 Patients must have an ECOG performance status ≤ 2 .
- 3.1.6 Patients must have adequate organ and marrow function as defined below (documented within 28 days of registration):
 - absolute neutrophil count $\geq 750/\text{mcL}$
 - platelets $\geq 50,000/\text{mcL}$
 - total bilirubin $\leq 2 \times$ institutional upper limit of normal (ULN)
 - AST(SGOT)/ALT(SPGT) $\leq 3 \times$ institutional ULN
 - creatinine $\leq 2 \times$ institutional ULN

NOTE: Patients who do not meet the above criteria because of disease involvement of the organ in question, or because of acute systemic illness due to lymphoma, may enroll with permission of the study PI and approval from the Data Monitoring Committee. We propose that this flexibility be allowed due to

the heterogeneity of the patient population, the wide range of complications seen in the initial presentation of EBV-related malignancy, and the frequent difficulty encountered in attempting to clearly document that organ dysfunction is the result of an underlying lymphoproliferative disorder.

In addition, patients with abnormal renal function may be included if the abnormal function is due to allograft dysfunction resulting from diagnosis of PTLD, or from reduction/cessation of immunosuppression aimed at treatment of PTLD.

3.1.7 Women of child-bearing potential and men must agree to use adequate contraception (hormonal or barrier method of birth control; abstinence) prior to study entry, for the duration of study participation, and for 90 days following completion of therapy. Should a woman become pregnant or suspect she is pregnant while participating in this study, she should inform her treating physician immediately.

3.1.9.1 A female of child-bearing potential is any woman (regardless of sexual orientation, having undergone a tubal ligation, or remaining celibate by choice) who meets the following criteria:

- Has not undergone a hysterectomy or bilateral oophorectomy; or
- Has not been naturally postmenopausal for at least 12 consecutive months (i.e., has had menses at any time in the preceding 12 consecutive months).

3.1.8 Patients must be free of any prior malignancies for ≥ 1 year.
*NOTE: The exception to this would be currently treated squamous cell and basal cell carcinoma of the skin, carcinoma *in situ* of the cervix, breast, or bladder, or surgically removed melanoma *in situ* of the skin (stage 0) with histologically confirmed free margins of excision. In addition, it is well-recognized that patients at highest risk for EBV-related lymphoma (ie, those with chronic immunosuppression) are also at high risk for various malignancies, both invasive and non-invasive. Therefore, exceptions may also be granted on a case-by-case basis, at the discretion of the PI with approval from the Data Monitoring Committee, for those patients with good clinical control of active malignancy, if the EBV-related lymphoma is considered to be a more immediate threat to the subject's health and/or life.*

3.1.9 Patients must have the ability to understand and the willingness to sign a written informed consent. All patients must have signed, witnessed informed consent prior to registration.

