6.2 Efficacy Definitions

6.2.1 Response and progression will be evaluated in Phases I and II using 2007 Revised Response Criteria for Malignant Lymphoma (modified).

6.2.1.1 Evaluable for objective response.

Only those patients who have measurable disease (at least 1cm) present at baseline, have received *at least three doses of brentuximab vedotin*, and have had their disease re-evaluated will be considered evaluable for response. These patients will have their response classified according to the definitions stated below. (Note: Patients who exhibit objective disease progression prior to the end of cycle 1 will also be considered evaluable.)

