6.2.2 Antitumor Effect

6.2.2.1 Response Criteria

Response criteria will be those specified by Cheson, et al [19] as the Revised Response Criteria for Malignant Lymphoma. Please refer to Table 6 for a tabular summary of the below definitions.

6.2.2.1.3 Complete Remission (CR):

The designation of CR requires the following (Table 6):

1. Complete disappearance of all detectable clinical evidence of disease and disease-related symptoms, if present before therapy.

2a. A post-treatment residual mass of any size is permitted as long as it is PET negative.

2b. If a pretreatment PET scan was negative, all lymph nodes and nodal masses must have regressed on CT to normal size (≤ 1.5 cm in their greatest transverse diameter for nodes > 1.5 cm before therapy). Previously involved nodes that were 1.1 to 1.5 cm in their long axis and more than 1.0 cm in their short axis before treatment must have decreased to ≤ 1.0 cm in their short axis after treatment.

3. The spleen and/or liver, if considered enlarged before therapy on the basis of a physical examination or CT scan, should not be palpable on physical examination and should be considered normal size by imaging studies, and nodules related to lymphoma should disappear. However, determination of splenic involvement is not always reliable because a spleen considered normal in size may still contain lymphoma, whereas an enlarged spleen may reflect variations in anatomy, blood volume, the use of hematopoietic growth factors, or causes other than lymphoma.

6.2.2.1.4

Partial Response (PR):

The designation of PR requires all of the following:

1. At least a 50% decrease in sum of the product of the diameters (SPD) of up to six of the largest dominant nodes or nodal masses. These nodes or masses should be selected according to all of the following: they should be clearly measurable in at least 2 perpendicular dimensions; if possible they should be from disparate regions of the body; and they should include mediastinal and retroperitoneal areas of disease whenever these sites are involved.

2. No increase should be observed in the size of other nodes, liver, or spleen.

3. Splenic and hepatic nodules must regress by $\geq 50\%$ in their SPD or, for single nodules, in the greatest transverse diameter.

4. With the exception of splenic and hepatic nodules, involvement of other organs is usually assessable and no measurable disease should be present.

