5. Bone marrow assessment is irrelevant for determination of a PR if the sample was positive before treatment. However, if positive, the cell type should be specified (eg, large-cell lymphoma or small neoplastic B cells). Patients who achieve a CR by the above criteria, but who have persistent morphologic bone marrow involvement, will be considered partial responders. When the bone marrow was involved before therapy and a clinical CR was achieved, but with no bone marrow assessment after treatment, patients should be considered partial responders.

6. No new sites of disease should be observed.
7. If the PET scan was positive before therapy, the post-treatment PET should be positive in at least one previously involved site.
8. If the pretreatment PET scan was negative, CT criteria should be used.

6.2.2.1.5 **Stable Disease (SD):**
Stable disease (SD) is defined as the following:

1. A patient is considered to have SD when he or she fails to attain the criteria needed for a CR or PR, but does not fulfill those for progressive disease (see “Relapsed Disease [after CR]/Progressive Disease [after PR, SD],” below).
2. The PET should be positive at prior sites of disease with no new areas of involvement on the post-treatment CT or PET.
3. If the pretreatment PET was negative, there must be no change in the size of the previous lesions on the post-treatment CT scan.

6.2.2.1.6 **Relapsed Disease (after CR)/Progressive Disease (after PR, SD)**
Lymph nodes should be considered abnormal if the long axis is more than 1.5 cm regardless of the short axis. If a lymph node has a long axis of 1.1 to 1.5 cm, it should only be considered abnormal if its short axis is more than 1.0. Lymph nodes $\leq 1.0 \times \leq 1.0$ cm will not be considered as abnormal for relapse or progressive disease.

1. Appearance of any new lesion more than 1.5 cm in any axis during or at the end of therapy, even if other lesions are decreasing in size. Increased FDG uptake in a previously unaffected site should only be considered relapsed or progressive disease after confirmation with other modalities. In patients with no prior history of pulmonary lymphoma, new lung nodules identified by CT are mostly benign. Thus, a therapeutic decision should not be made solely on the basis of the PET without histologic confirmation.

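### The 1 cm measurable-disease threshold lies below the protocol's own abnormal-node size, so the CT response category of a patient with one small node is not properly defined

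*Combined protocol and SAP*

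**What the plan says.** Entry (section 3.1.3): "Patients must have bi-dimensionally measurable disease (at least 1 cm"). A note there keeps patients with fully resected disease eligible and evaluable for everything except objective response.

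Response set (section 6.2.1.1): "Only those patients who have measurable disease (at least 1cm) present at baseline", with at least three brentuximab vedotin doses and a re-evaluation, are evaluable for response. Neither section says which axis must reach 1 cm, or separates nodes from extranodal lesions.

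Node size (section 6.2.2.1.6, relapsed or progressive disease): "Lymph nodes should be considered abnormal if the long axis is more than 1.5 cm regardless of the short axis". For a long axis of 1.1-1.5 cm, "it should only be considered abnormal if its short axis is more than 1.0". Nodes no larger than 1.0 cm in either dimension "will not be considered as abnormal for relapse or progressive disease".

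CR (section 6.2.2.1.3): item 1 requires "Complete disappearance of all detectable clinical evidence of disease and disease-related symptoms, if present before therapy". Item 2b, for a negative pretreatment PET, says "all lymph nodes and nodal masses must have regressed on CT to normal size". It then gives two numeric targets. Nodes above 1.5 cm must come down to 1.5 cm or less. Nodes 1.1-1.5 cm long with a short axis above 1.0 cm must come down to at most "1.0 cm in their short axis after treatment".

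PR needs a 50% fall in the sum of the products of the diameters (SPD). SD item 3 describes unchanged lesion size on CT when the pretreatment PET was negative. Footnote 2 of the Time and Events Table prefers PET/CT but allows CT alone at any time point.

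**The concern.** A response criterion presupposes a lesion that is abnormal at baseline. Here the threshold for being counted is lower than the threshold for being abnormal, so some evaluable patients can start with a node that is already at the CT end point for CR. In such a patient a CR says little about the treatment.

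It matters wherever response means CR or PR: the Phase II stopping rule in section 7.5, the CR/PR versus SD/PD comparisons in sections 9.2.2 and 9.2.4, and the overall response rate (ORR) tested against 50% in section 10.1.2 if that is read as CR plus PR. Patients scored as responders for this reason push the observed rate up, and weaken both the futility look and the final test.

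**Working it through.** **Step 1. Which nodes fall in the gap.** I compared the 1 cm threshold with the abnormal-node rule on a 0.1 cm grid.

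| Reading of the 1 cm threshold | Nodes that are eligible but normal-sized |
|---|---|
| Long axis only | Long axis 1.0-1.5 cm, short axis 1.0 cm or less |
| Both dimensions | Long axis 1.0-1.5 cm, short axis exactly 1.0 cm |

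A node 1.1-1.5 cm long with a short axis above 1.0 cm is abnormal and has a CR target, so it is not affected. The width of the gap depends on the axis that the protocol does not name.

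**Step 2. How a 1.4 x 1.0 cm node is classified** (only lesion, pretreatment PET negative or not done).

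- Neither numeric target in CR item 2b applies: the long axis is not above 1.5 cm and the short axis is not above 1.0 cm.
- Shrinks to 1.3 x 1.0 cm: the SPD goes from 1.40 to 1.30 cm², a fall of 0.10/1.40 = 7%. PR would need 0.70 cm² or less. Yet the node has become smaller and is of normal size, so the CR size wording is met.
- Unchanged: it meets the normal-size end state, but it also fits SD item 3. The text does not settle which applies.
- No separate CR rule is given for a patient who has no PET at all.

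**Step 3. Reproduce the plan's design figure.** Inputs from section 10.1.2: p0 = 0.50, p1 = 0.70, alpha < 0.05, beta < 0.20, stop at 8 or fewer responses in 15. An exact binomial search for the optimal two-stage design gives 8/15 then 26/43, with type I error 0.0499 and power 0.804. Expected sample size under p0 is 15 + P(X ≥ 9 | 15, 0.50) × (43 − 15) = 15 + 0.3036 × 28 = 23.5, which rounds to the stated 24. The documents do not state a 43-patient stage, and section 10.2 plans 24 Phase II patients, so the sensitivity below uses 24.

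**Step 4. Sensitivity.** Two inputs are assumptions:

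- The share m of evaluable patients scored as responders whatever the treatment does. The documents give no figure.
- The final cut-off for N = 24, which is not stated. I take 17 or more, the lowest that keeps type I error below 0.05 (16 or more gives 0.072).

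The null response rate becomes p = 0.50 + 0.50m. With X1 ~ Bin(15, p) and X2 ~ Bin(9, p), type I error is the sum over x = 9 to 15 of P(X1 = x) × P(X2 ≥ 17 − x).

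| Share m | p | Chance of passing the 8/15 look | Type I error, N = 24 |
|---|---|---|---|
| 0 | 0.500 | 0.304 | 0.032 |
| 2% | 0.510 | 0.332 | 0.039 |
| 1 in 24 | 0.521 | 0.363 | 0.049 |
| 5% | 0.525 | 0.375 | 0.053 |
| 10% | 0.550 | 0.452 | 0.085 |
| 20% | 0.600 | 0.610 | 0.190 |

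Section 7.5 gives a different first-stage rule (four or fewer of 15). That is a separate inconsistency; the figures here use the rule in section 10.1.2.

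**The case against.** A reader might infer that a patient with an already normal-sized node is a guaranteed responder, called CR with no shrinkage at all. The documents do not support that. Item 2b and Table 6 both speak of nodes having regressed, CR item 1 requires clinical evidence of disease to disappear, and an unchanged node matches the SD wording. What stands is narrower: the category of an unchanged node is ambiguous, and a very small decrease is enough for the CR size wording.

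A reader might also infer that the primary endpoint as written is biased by this threshold. Section 2.3.2 counts SD as well as PR and CR as response, so under that wording the CR or SD label changes nothing. The issue bites only in the CR/PR-based uses.

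The route is also narrow. It needs a sole small node, no extranodal disease, and a baseline PET that is negative or not done, while PET/CT is the preferred method. The PFS definition in section 6.2.3 even calls PET/CT after induction and consolidation mandatory, although footnote 2 permits CT alone. If both dimensions must reach 1 cm, only nodes with a short axis of about 1.0 cm are left. The abnormal-node text sits under relapse and progression, so it is not formally a baseline definition, but item 2b uses the same cut-offs.

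These limits reduce the likely size. They do not remove the mismatch.

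**Conclusion.** The mismatch is in the text: disease can be measurable and response-evaluable while normal-sized by the protocol's own criteria, and on CT such a node can be scored CR after trivial shrinkage or fit two categories if unchanged. It bears on the CR/PR-based ORR, not on the endpoint as worded in section 2.3.2.

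The size is unknown. At an assumed 1 in 24 affected patients, type I error moves from 0.032 to about 0.049, still under the nominal 0.05. At 10% it is 0.085. Both figures rest on the assumed cut-off of 17 of 24, on the 8/15 look, and on every affected patient being scored as a responder, which makes them upper-end values for a given share. This is a low-cost improvement to the response definition, not a flaw that undermines the trial.

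**What to change.** In section 6.2.1.1, for response evaluability, require one of the following at baseline:

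- nodal disease that is abnormal by the rule in section 6.2.2.1.6 (long axis above 1.5 cm, or 1.1-1.5 cm with a short axis above 1.0 cm);
- smaller nodal disease that is PET-positive at baseline and re-staged by PET;
- an extranodal lesion of at least 1 cm, with the axis named.

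Patients who have only smaller nodes stay eligible and are evaluable for all endpoints except objective response, as section 3.1.3 already does for resected disease. Name the axis in section 3.1.3 too.

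Cost: a short amendment, and a few patients no longer count toward the ORR. Section 4.9 should say whether such a patient is replaced in Phase II, because its present replacement rule does not cover them. Small-node patients who can only have CT would fall outside the response set.

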4.9 Patient Replacement

During Phase I, all three patients enrolled at the starting dose level must be observed for one cycle (21 days), at which point the study will be temporarily suspended for toxicity evaluation, before which it may either be reopened for an additional cohort (at either the same dose or a lower dose), or proceed to Phase II (as outlined in sections 4.1.2 and 4.1.3). Any DLT noted at any point after treatment begins (up till the end of the DLT evaluation period) shall count toward the total number of DLT, and patients are not replaced. An exception will be made for those patients who are enrolled but, for whatever reason, never receive treatment; such patients should be replaced. If a patient is withdrawn from the study within 21 days of starting therapy, for whatever reason, but without experiencing a DLT prior to withdrawal, an additional patient may be added to that dose level. Patients missing more than three weeks' worth of doses due to toxicity will not be replaced since these patients will be considered to have experienced a dose limiting toxicity.

During Phase II, any patient who is enrolled but not treated on the study, or who completes fewer than two total cycles of therapy and is withdrawn for any reason except POD or toxicity, shall be replaced.

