10.1.2 Phase II

Our null hypothesis is that the combination of rituximab and brentuximab vedotin will yield no difference in the rate of ORR as compared to that observed with historical treatments. The historical ORR for both PTLD and EBV-related

lymphoma of the elderly, when treated with rituximab (with or without chemotherapy is estimated at approximately 50% [1, 2]. Therefore, the optimal two-stage design to test the null hypothesis that $P=0.50$ versus the alternative that $P>=0.70$ (the hypothesized ORR to rituximab plus brentuximab vedotin) has an expected sample size of 24. Under these conditions, if the combination is actually not significantly more efficacious, there is a <0.05 probability (also known as the alpha value) of concluding that it is. If the combination is actually significantly more efficacious, there is a <0.20 probability (also known as the beta value) of concluding that it is not. Early futility may be declared, such that if eight or fewer responses are observed among the first 15 patients enrolled, the trial will be stopped and considered no more efficacious than therapy with rituximab alone.

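### Fully resected patients cannot be scored for objective response, yet they fill places among the first 15 and the 24 Phase II patients, which raises the chance of a false futility stop.

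*Combined protocol and SAP*

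**What the plan says.** Section 3.1.3 requires bi-dimensionally measurable disease of at least 1 cm, then adds a note: "Patients with fully resected disease are eligible, and will be evaluable for all toxicity and efficacy endpoints except objective response". Section 6.2.1.1 agrees, opening its definition of the response-evaluable set with "Only those patients who have measurable disease (at least 1cm) present at baseline".

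The decision counts do not refer to that set:

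- **Interim rule, 10.1.2 (same rule in the synopsis):** "if eight or fewer responses are observed among the first 15 patients enrolled, the trial will be stopped".
- **Interim rule, 7.5:** stop if four or fewer of the first 15 patients treated have a CR or PR. This is a different boundary.
- **Phase II size, 10.2:** 24 patients are to be enrolled.
- **Replacement, 4.9:** a Phase II patient who is enrolled but not treated, or who "completes fewer than two total cycles of therapy and is withdrawn for any reason except POD or toxicity, shall be replaced".

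Exclusion 3.2.3 bears on how many resected patients can enter. Prior surgery for lymphoma is disqualifying unless it was done for tissue diagnosis, or urgently for a threat to life, limb or organ function.

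**The concern.** A fully resected patient is known at registration to be unable to contribute an objective response. If that patient stays on treatment, 4.9 gives no replacement, and the patient keeps a place among the first 15 enrolled and among the 24.

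The futility rule is a fixed count of responses, so a patient who cannot add to the count lowers the chance of passing exactly as a non-responder would. Leaving such patients out of the response denominator does not help at the interim: a threshold built for 15 informative patients would then be applied to 14 or 13, and the probability of stopping is the same.

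What is at stake is the only efficacy interim stated for Phase II. An active regimen could be abandoned because of who was enrolled and not because of how the regimen performed. The loss is set by eligibility, before any treatment is given.

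**Working it through.** **Inputs.** From 10.1.2: null rate 0.50, alternative 0.70, alpha below 0.05, beta below 0.20, stop at eight or fewer responses in 15. From 7.5: stop at four or fewer in 15. Response is taken as CR plus PR. The number k of resected patients among the first 15, and the resected share f, are assumptions.

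**Step 1: reproduce the plan's figure.** An exact binomial search for the optimal two-stage design under these inputs gives stage 1 of 8/15 and a final boundary of 26/43, with alpha 0.0499 and power 0.804. Under the null rate the probability of early stopping is 0.696, so the expected size is 15 + (1 − 0.696) × 28 = 23.5. This agrees with the plan's statement that the design "has an expected sample size of 24", and it confirms that 8/15 is the boundary belonging to the stated hypotheses. The 26/43 boundary is derived here; the protocol does not state it. Whether 24 is adequate as the total enrolled is a separate matter.

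**Step 2: false-stop probability with k resected patients.** Only 15 − k patients can respond, so

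P(stop | k) = P(X ≤ c), X ~ Binomial(15 − k, 0.70), with c = 8 (10.1.2) or c = 4 (7.5).

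Worked case, k = 1 and c = 8: the probabilities of 9, 10, 11, 12, 13 and 14 responses in 14 are 0.1963, 0.2290, 0.1943, 0.1134, 0.0407 and 0.0068. They sum to 0.7805, so P(stop) is 0.2195 (21.9% from the unrounded 0.21948).

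| Resected among first 15 (assumed) | Stop at ≤8 (10.1.2, synopsis) | Stop at ≤4 (7.5) |
|---|---|---|
| 0 | 13.1% | 0.07% |
| 1 | 21.9% | 0.17% |
| 2 | 34.6% | 0.40% |

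With three resected patients the 7.5 rule still gives only 0.95%.

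**Step 3: average over an assumed share.** If each enrolled patient is resected with probability f, independently, each of the 15 places yields a response with probability 0.70 × (1 − f), and P(stop) = P(Binomial(15, 0.70(1 − f)) ≤ 8).

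| Assumed share f | Response probability per place | P(stop), ≤8 rule |
|---|---|---|
| 0% | 0.700 | 13.1% |
| 2% | 0.686 | 15.9% |
| 5% | 0.665 | 20.7% |
| 10% | 0.630 | 30.0% |

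**Step 4: direction.** At a true rate of 50%, one resected patient moves the stop probability under the 8-of-15 rule from 69.6% to 78.8%. The error runs one way, towards stopping; it does not make an inactive regimen look active.

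**The case against.** Several points on the other side are sound.

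- **Few patients may be affected.** Exclusion 3.2.3 admits only patients left free of measurable disease by diagnostic or urgent surgery. It is not a cap, but it narrows the group. A reader might infer from the binomial formula that the interim becomes a coin toss: with three resected patients it gives 50.7%. That needs 20% of the first 15 to be resected, which no passage supports.
- **The size depends on which boundary governs.** Under 7.5 the effect is negligible. The 8-of-15 rule stands in both the statistical section and the synopsis and matches the stated hypotheses, so it is the natural reading, but the conflict is real. Section 10.1.2 also says first that futility may be declared and then that the trial will be stopped, so how binding the rule is remains unclear.
- **The counted endpoint is unsettled.** Section 2.3.2 includes SD in response, while 7.5 and 9.2.2 use CR and PR. The figures above need CR plus PR. On either definition, 3.1.3 makes resected patients non-evaluable.

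Two further inferences are tempting but unsupported. One is that resected patients dilute the final response rate, for instance to 0.70 × 21/24 = 61% with three among 24. Sections 3.1.3 and 6.2.1.1 remove them from the response analysis, so what is lost at the end is precision. The other is that they have no path through 4.1.3 because it is keyed to CR, PR, SD and PD. Section 3.1.3 excludes them from an endpoint; it does not say they cannot be re-staged.

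**Conclusion.** The gap is real and should be fixed. The plan admits patients who cannot be scored on the primary endpoint, counts them towards a fixed-threshold interim and the enrolment target, and does not replace them. At a true response rate of 70% under the 8-of-15 rule, one such patient among the first 15 raises the false-stop probability from the design value of 13.1% to 21.9%, and two raise it to 34.6%.

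Confidence is high in the wording gap and the arithmetic, and limited in the practical size. The size rests on assumed numbers of resected patients, on response meaning CR plus PR, and on 10.1.2 governing over 7.5. With numbers that are probably small and an effect below 1% under one of the two stated boundaries, this is a worthwhile and inexpensive correction. It is not a flaw that invalidates the design.

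**What to change.** - **Define the counts.** In 10.1.2, the synopsis, 7.5 and 10.2, make the 15 and the 24 the first 15 and the total of 24 treated Phase II patients with measurable disease at baseline.
- **Link to 6.2.1.1.** State how this set relates to the response-evaluable set there, which also asks for at least three brentuximab vedotin doses and a re-evaluation, with an allowance for early progression. Otherwise a second, unlinked response population is created.
- **Place resected patients.** State in 3.1.3 that they do not occupy a primary-endpoint slot and are reported for toxicity, PFS, OS and the remaining secondary endpoints only.
- **Reconcile the boundaries.** Make 7.5 and 10.1.2 give one interim rule.

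With the 15 so defined, the false-stop probability at 70% returns to 13.1%.

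**Cost.** Wording, plus one of two consequences:

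- If resected patients are enrolled in addition, the total rises slightly. At an assumed share of 10%, 24/0.90 = 26.7, so 27 enrolled give 24 with measurable disease. Check this against the total of 33 in section 3.0: it leaves 33 − 24 = 9 places for Phase I and any additional patients together, and the synopsis allows 3 to 9 in Phase I.
- Otherwise, close the exception for the rest of Phase II. Restricting it to Phase I would amount to the same thing, since 4.1.1 records that the RP2D was established on 3/12/2014.
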